Endocrowns are considered as effective restorations for molars that have undergone endodontic treatment offering better fracture resistance and stress distribution, offer excellent strength for cuspal overlays, it can be used as a final restoration for primary molars preserve tooth structure, and maintain periodontal health⁽¹³⁾.

Up to our knowledge, there is no study evaluate the clinical performance, bacterial adherence, assessment of dental plaque and gingival status of endocrowns and Bioflex crowns as a new restorative modality in Pulpotomized primary molars compared with prefabricated ZCs, and the parental satisfaction toward the three restorations at the end of the 12 month follow-up

Aim of the study

This study will be conducted to evaluate clinical performance, parent's satisfaction, gingival health and bacterial effects of Bioflex crowns & Endocrowns compared to ready-made zirconia Crowns on Pulpotomized primary molars

Patients and Methods

Study Design:

This study will be designed as a randomized clinical trial

Sample Size calculation: ^(7,13)

This study will be conducted to evaluate Clinical performance, bacterial adherence, assessment of gingival health and patient satisfaction of LS2 endocrowns and Bioflex crowns compared with prefabricated zirconia

crowns as a restoration of Pulpotomized primary molars. Assuming there is no difference between groups (equivalence trial), if there is truly no difference between the standard and experimental treatments, then 22 patients in each group are required to be 80% sure that the limits of a two-sided 95% confidence interval will exclude a difference in means of more than 0.6. This number is to be increased to 24 in each group to compensate for possible losses during follow up. Sample size was calculated by sealed envelope power calculator.

Study Setting and Population:

This study will involve children with 72 primary molars who require Pulpotomy treatment at the Pedodontics and Oral Health Department, Faculty of Dental Medicine (Boys, Cairo), Al-Azhar University.

Subject grouping:

The involved primary molars (n= 72) will be divided randomly into 3 groups (n=24) according to the type of the final restoration for Pulpotomized molars as the following

- **Group A:** will be restored with endocrown (study group)
- **Group B:** will be restored with prefabricated Bioflex crown (study group).
- **Group C:** will be restored with prefabricated zirconia crown (control group).

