- Clinical performance and oral status will be assessed at follow-up periods of 3 (T1), 6 (T2), and 12 (T3) months. At the end of the follow-up (T3), parent's satisfaction analysis toward the color, shape, and size of three restorations will be adopted to directly evaluate their satisfaction toward their children's restorations. Parents' responses were rated on a 5-point Likert-type scale.

Microbiological analysis: ⁽⁹⁾

- The swabs will be collected before preparation of crowns, 3 months, 6 months and 12 months after cementation.
- The number of Streptococcus Mutans, lactobacillus will be digitally counted.
- Swabs will be taken from occlusal surface by means of the tips of sterile cotton
- All specimens were transported immediately to microbiological lab.
- Swabs will be taken from occlusal surface by means of the tips of sterile cotton.
- Samples will be preserved in a transporting medium tube containing 9ml thioglycolate broth medium.
- The number of Streptococcus Mutans, lactobacillus will be digitally counted.

Data Management and Analysis

Data will be analyzed using IBM SPSS advanced statistics (Statistical Package for Social Sciences), version 27 (SPSS Inc., Chicago, IL). Numerical data will be described as mean and standard deviation or median and range. Data will be explored for normality using Kolmogorov-Smirnov test and Shapiro-Wilk test. Comparisons between 3 groups for normally distributed numeric variables will be done using the ANOVA while for non-normally distributed numeric variables will be done by Kruskal Wallis test. An equivalence limit will be checked in the difference between groups. Categorical data will be described as numbers and percentages and comparisons will be done by chi square test or fisher exact as appropriate. A p-value less than or equal to 0.05 will be considered statistically significant. All tests will be two tailed.

References

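### Two normality tests with no deciding rule choose between ANOVA and Kruskal-Wallis, and the Kruskal-Wallis branch gives no estimate to set against a margin defined on means

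*Combined protocol and SAP*

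**What the plan says.** Under Data Management and Analysis, the plan states: "Data will be explored for normality using Kolmogorov-Smirnov test and Shapiro-Wilk test". The result selects the test. One branch reads: "Comparisons between 3 groups for normally distributed numeric variables will be done using the ANOVA". Variables that fail the screen go to Kruskal-Wallis instead. Summaries follow the same either/or pattern: "Numerical data will be described as mean and standard deviation or median and range". A separate sentence, attached to neither branch, adds: "An equivalence limit will be checked in the difference between groups".

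Under Sample Size calculation the trial is framed as an equivalence trial. The criterion is that the "two-sided 95% confidence interval will exclude a difference in means of more than 0.6", with 22 per group for 80% power, raised to 24 for losses.

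The plan does not state:
- which normality test decides when they disagree, or at what level;
- whether they are applied per group, to pooled data or to residuals;
- whether the choice is made once or anew for each outcome and visit;
- how the plaque index (PI) and gingival index (GI) are scored, or whether Likert ratings count as numeric or categorical;
- which outcome, pair of groups, visit and interval method the equivalence check uses.

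**The concern.** The method for each numeric outcome is settled only after the data are seen, and two tests without a deciding rule leave the analyst a choice. If PI and GI are treated as numeric, the choice recurs often: 2 indices × 3 visits + 2 bacterial counts × 4 time points + 1 preparation time = 15 occasions, before satisfaction is considered. One outcome could be reported by ANOVA with means at 3 months and by Kruskal-Wallis with medians at 12 months, which makes the visits hard to compare.

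The objective matters too. A margin of 0.6 on a difference in means needs an estimated difference in means with an interval. An outcome sent to Kruskal-Wallis and summarised by median and range comes with neither.

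**Working it through.** **Inputs from the plan.** Three groups, 22 per group (24 with losses), visits at 3, 6 and 12 months, margin 0.6, two-sided 95% interval, 80% power. The plan gives no distributions, SD or index scoring, so every distribution below is an assumption.

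**Step 1: the plan's own figure.** For equivalence with a true difference of zero, n = 2·SD²·(z₀.₉₇₅ + z₀.₉₀)² / 0.6², where (1.960 + 1.282)² ≈ 10.507. With SD 0.60, n = 2 × 0.36 × 10.507 / 0.36 = 21.01, rounded up to 22. SD 0.55 gives 18, SD 0.70 gives 29 and SD 1.0 gives 59. The stated 22 therefore implies an SD of about 0.60-0.61, which the plan does not give. The derivation is wholly on the scale of means.

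**Step 2: how the two tests behave.** Simulated samples of 22, both tests at 0.05, with the Lilliefors-corrected form of Kolmogorov-Smirnov (KS):

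| Assumed distribution | KS rejects | Shapiro-Wilk rejects | Tests disagree |
|---|---|---|---|
| Normal | 4% | 5% | 5% |
| Single 0-3 score | 100% | 100% | 0% |
| Mean of four 0-3 scores (two variants) | 38%, 58% | 19%, 39% | 26%, 30% |
| Likert, skewed | 100% | 100% | 0% |
| Likert, symmetric | 88% | 77% | 20% |
| Lognormal, log-SD 0.5 | 36% | 56% | 26% |
| Lognormal, log-SD 1.0 | 84% | 96% | 12% |

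Disagreement and near-certain rejection thus fall mostly on different outcomes. At trial level, calling an outcome non-normal if any of the three groups fails, the two tests lead to different analyses in about 30% of trials for a four-site mean and about 20% for moderately skewed counts. For coarse scores and skewed Likert items the figure is 0%, and Kruskal-Wallis is always used. A separate run at 24 per group gave 26% for a four-site mean, 29% for mild skew and 16% for moderate skew.

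These figures depend on details the plan leaves open. With uncorrected KS, per-sample disagreement ranges from 5% to 79% and reaches coarse scores as well. With 66 pooled values and the corrected form, it is 0% and 24% for the two averaged indices.

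**Step 3: switching between visits.** Take Shapiro-Wilk alone, the any-group rule, and visits treated as independent. For normal data, P(any group fails) = 1 − 0.953³ ≈ 0.134. P(method not the same at all three visits) = 1 − 0.134³ − 0.866³ ≈ 0.35; simulation gave 36%. For averaged indices, simulation gave 52% and 75%, and for single 0-3 scores 0%. The same children are seen at each visit, so independence is a simplification.

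**Step 4: can the 0.6 limit be checked on non-normal scores?** With 22 per group and 20,000 simulated pairs of samples, the 95% t-interval for a difference in means covered the truth in 95.1% (0-3 score) and 95.2% (0-2 score). Further runs gave 94.9% for a 0-3 score, 95.3% for a four-site mean and 94.4% for a skewed 5-point rating. It can.

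**Step 5: effect on false positives.** With three equal groups, choosing the test by normality screening gave 3.6-6.5% false positives across assumed distributions. Always reporting the smaller of the ANOVA and Kruskal-Wallis p-values gave 4.7-7.3%. A second set of runs gave 4.6-5.7% and 5.7-6.7%, and the two tests differed on significance in 1-4% of trials. These runs cover the null case only.

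**The case against.** The strongest reply is that little damage follows. The equivalence check is its own sentence, tied to neither branch, and the sample-size section already names a 95% interval on means, which can be computed whichever overall test is run. The ANOVA F test does not check a margin either. The false-positive cost is within a few percentage points even under deliberate selection, and for coarse scores the two tests agree, so there is nothing to choose. All of this stands.

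It also rules out three stronger readings. A reader might infer that the 0.6 limit cannot be checked for outcomes sent to Kruskal-Wallis. The documents do not support that, because the check is listed separately and Step 4 shows the interval works. A reader might also infer that the rule materially inflates type I error; Step 5 does not show this. Finally, a reader might assume that the margin belongs to PI, GI or satisfaction. The plan never names its outcome, and Likert ratings treated as categorical would go to chi-square or Fisher tests and never meet the normality screen.

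The reply does not remove the missing rule, or the mismatch between a rank test with medians and a margin on means.

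**Conclusion.** The point holds as a modest, inexpensive improvement. The absence of a deciding rule can be read directly from the text and needs no simulation. Its size, about 20-30% of three-group comparisons routed differently for averaged indices and moderately skewed counts, rests on assumed distributions, a 0.05 screening level, per-group testing with an any-group rule, and the corrected form of KS. Coarse scores and skewed Likert items, if numeric, go consistently to Kruskal-Wallis under the same assumptions.

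The main consequence is a plan that can report different kinds of summary for one outcome across visits, and whose rank branch produces nothing to compare with 0.6. No stated figure changes. The missing SD and the unnamed outcome behind the margin are separate gaps.

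**What to change.** Delete the normality tests as the selector and fix the following before data are seen:

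- **The outcome that carries the 0.6 limit, and PI and GI:** a two-sided 95% interval for the difference in means, from a linear model, Welch or bootstrap (one of these, named), for endocrown versus zirconia and Bioflex versus zirconia at every visit. Compare it with ±0.6 only for the outcome for which the margin was set, and name that outcome.
- **Bacterial counts, preparation time and satisfaction:** one method each, for example log10 counts. The exact choice is a matter of preference; fixing it in advance is what matters.
- **Kruskal-Wallis:** keep as a sensitivity check.

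The cost is slightly more analysis wording, with no change to data collection, sample size or patient procedures. The downside is that a rank test is no longer the main result for skewed outcomes, which some readers may prefer to see first.

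### Plaque index, gingival index and bacterial counts are repeated on each molar at 3, 6 and 12 months, but the plan names only tests between three groups, with no primary visit and no method that links the visits.

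*Combined protocol and SAP*

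**What the plan says.** Under Observations, the Clinical Performance Assessment list includes PI and GI, and the schedule reads: "Clinical performance and oral status will be assessed at follow-up periods of 3 (T1), 6 (T2), and 12 (T3) months". Under Microbiological analysis: "The swabs will be collected before preparation of crowns, 3 months, 6 months and 12 months after cementation". Each molar therefore yields three follow-up values of PI, GI, S. mutans and lactobacillus, and each bacterial outcome also has one value from before treatment.

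Under Data Management and Analysis, the method for numeric outcomes is: "Comparisons between 3 groups for normally distributed numeric variables will be done using the ANOVA". Kruskal-Wallis is the alternative when normality fails. The significance rule is: "A p-value less than or equal to 0.05 will be considered statistically significant. All tests will be two tailed". The section adds that an equivalence limit will be checked, but gives no outcome, visit or method for that check. It has no visit or group-by-visit term, no repeated-measures method, no covariate, no primary visit, and no statement on whether visits are analysed separately or together.

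**The concern.** The section does not say how three correlated values from one molar become one comparison between crowns. If each visit is tested alone, an outcome can differ at 3 months and not at 12, and the plan has no rule for which result counts. Each extra visit is also another chance of a false positive at the 0.05 level. A molar seen at 3 and 6 months but not at 12 contributes nothing to the 12-month test. The pre-preparation swab is collected, but no between-group comparison uses it. The trial is planned with 22 evaluable molars per group and an equivalence aim, so the choice of visit and the handling of partial follow-up can decide the conclusion.

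**Working it through.** **Inputs from the documents.** Three groups; 22 molars per group, raised to 24 for losses; visits as quoted; two-sided 0.05; 80% power; a limit of 0.6 on the difference in means; true difference zero ("Assuming there is no difference between groups (equivalence trial").

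**Inputs assumed.** Within-molar correlation rho between visits, 0.3 to 0.7. Correlation r between the pre-preparation and follow-up log counts, 0.3 to 0.7. SD as derived in step 1. The documents give none of these.

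**1. The plan's own figure.** Sample Size calculation gives 22 per group for 80% power; its criterion is: "the limits of a two-sided 95% confidence interval will exclude a difference in means of more than 0.6". For equivalence with no true difference, n per group = 2 × [SD × (1.960 + 1.282) / 0.6]². The SD is not stated, so 22 cannot be reproduced from the document alone. It follows if the SD is about 0.60 to 0.614; an SD of 0.55 gives 18, 0.65 gives 25 and 0.70 gives 29. Steps 2 to 4 do not depend on this SD.

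**2. One test per visit.** Simulation (40,000 trials per setting, three groups of 22, equal correlation between visits, no true difference) gives close to 0.05 at each visit, so each test is valid alone. The chance of at least one p-value at or below 0.05 over the three visits is:

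| rho | at least one false positive |
|---|---|
| 0.3 | 14.2% |
| 0.5 | 12.8% |
| 0.7 | 11.0% |

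For reference, independent visits would give 1 − 0.95³ = 14.3%. These figures are per outcome.

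**3. Visits pooled as if independent.** The variance is understated by the factor 1 + 2 × rho, which is 1.6, 2.0 and 2.4 at rho 0.3, 0.5 and 0.7. The standard error is therefore too small by factors of 1.26, 1.41 and 1.55. With two degrees of freedom between groups, the type I error is about exp[−5.99 / (2 × factor)]: 15%, 22% and 29%. The simulation gives 16%, 23% and 29%.

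**4. Using the pre-preparation count.** Adjustment leaves 1 − r² of the variance: 0.91, 0.75 and 0.51 at r = 0.3, 0.5 and 0.7. The reduction is 9%, 25% and 49%.

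**5. Averaging the three visits (illustrative).** The variance of a molar's mean over T1-T3, relative to one visit, is (1 + 2 × rho)/3 = 0.53, 0.67 and 0.80. With the assumed SD of 0.614, the SE of a group difference at one visit is 0.614 × √(2/22) = 0.185. For the average it is 0.135, 0.151 and 0.166. Equivalence power, 2Φ(0.6/SE − 1.96) − 1, is 80% at one visit and 99%, 96% and 90% for the average.

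**6. What averaging could hide (illustrative).** Suppose the true differences are 0, 0.3 and 0.6 at T1, T2 and T3, so that the crowns reach the limit at 12 months. The average difference is 0.3. At rho 0.5, equivalence on the average is declared when the estimate is below 0.6 − 1.96 × 0.151 = 0.304, which has probability about 51% (60% at rho 0.3, 44% at rho 0.7). At T3 alone the estimate must be below 0.6 − 1.96 × 0.185 = 0.237 when the truth is 0.6, which has probability 2.5%.

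**The case against.** The strongest defence is that the plan does nothing invalid. It labels the visits T1, T2 and T3, which suggests separate tests, and each is sound at its own visit. This stands. A reader might infer that the three visits will be pooled and that the type I error is therefore 22% or more. The documents do not support that: nothing in Data Management and Analysis proposes pooling, so step 3 is only a warning about an option left open.

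It can also be said that the ANOVA named might be a repeated-measures one. The text ties it to comparing three groups and its alternative is Kruskal-Wallis, a one-factor test for independent groups, so this reading is weak. If it was intended, it still has to be written down.

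A further objection concerns precision. A reader might infer from step 5 that the plan forfeits a rise in equivalence power from 80% to 96%. That gain belongs to the year average, which is a different target from the 12-month difference. It also rests on an SD the documents do not give and on a limit of 0.6 that they do not tie to PI, GI or the counts. The limit could belong to parent satisfaction, which is measured only at 12 months and would gain nothing from repeated visits. With complete data, a mixed model with group by visit and unstructured covariance gives essentially the same T3 contrast and SE as a test at T3. This objection stands, and step 6 shows why the average should not be the headline in an equivalence trial.

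Finally, raising 22 to 24 already allows for some losses. It does, but it does not say how a molar with one missed visit is analysed.

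**Conclusion.** The gap is real and should be closed before analysis. It does not make the plan's single-visit tests wrong. The plan leaves the longitudinal comparison of four repeated outcomes undefined. Read naturally, it gives three unlinked answers per outcome, with an 11-14% chance of at least one false positive at an assumed within-molar correlation of 0.7 to 0.3. It also excludes molars from the visits they miss and leaves the pre-preparation count unused.

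The benefit of a linked analysis is one main answer per outcome, retention of molars with partial follow-up and, for the counts only, a variance reduction of about 9-49% at an assumed baseline correlation of 0.3 to 0.7. For PI and GI at 12 months with complete data, little gain in precision should be expected. Neither the pooling error nor the 96% power figure should be cited as a property of this plan.

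**What to change.** In Data Management and Analysis, replace the separate tests for PI, GI and the two bacterial counts with one repeated-measures model per outcome:

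- Use SPSS MIXED, with group, visit and group by visit as fixed effects and a within-molar covariance.
- For S. mutans and lactobacillus, analyse log counts with the pre-preparation log count as covariate, and state in advance how zero counts are handled.
- For PI and GI, use an ordinal or rank-based repeated-measures version if the scores are coarse or skewed.
- Name 12 months (T3) as the primary visit. Report each new crown against zirconia at T3, with a 95% confidence interval from the model, as the main contrast.
- Report the T1-T3 average and the 3- and 6-month contrasts as secondary.
- State that every molar with any follow-up value is included, and that this relies on missed visits being explained by the observed data.

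The cost is a few lines of text, slightly more analysis work and model assumptions to check. No new data or visits are needed.

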- Abrasive rubber tip will be used to smoothening and rounding the internal angles giving a polished and smoothed preparation.
- Endocrown will be manufactured using CAD/CAM technology
- internal wall of crown will be treated with etchant material, rinsed, dried then silane coupling agent

- Dual-cure resin cement will be applied on the crown fitting surface for endocrown cementation.

Group B: Preformed Bioflex crowns ⁽¹⁰⁾

According to manufacturer instruction the preparation will be as the follow:

- Light -cured glass ionomer filling of adequate thickness will be applied over the ZOE to seal the cavity before preparation
- A digital caliper will be used to measure a mesio-distal dimension of tooth then suitable sized preformed crown will be selected.
- Tooth preparation will be carried out with a tapered diamond bur for occlusal reduction by 1–1.5 mm, including the central groove.
- The proximal preparation will be around 0.5 mm to clear the contact area
- Placement of the crown will be achieved by a snug fit followed by contouring using a Hover's plier.
- Crown cementation will be carried out using glass ionomer cement and removal of excess cement using floss or explorer.

Group C: performed zirconia crowns ^(10, 12, 13)

- Light -cured glass ionomer filling of adequate thickness will be applied over the ZOE to seal the cavity before preparation.
- A digital caliper will be used to measure a mesio-distal dimension of tooth then suitable sized preformed crown will be selected.

- A diamond bur will reduce the occlusal surface by 1.5–2 mm
- Interproximal contacts will be prepared with a tapered fissure bur. About 1–2 mm sub gingival preparation will be performed
- The selected crown will be placed and checked.
- The passive fit of the crown will be assessed and will be luted with glass ionomer cement.
- Consistent firm finger pressure will be applied during cementation.

Observations:

Clinical Performance Assessment ^(10,12)

- Retention, marginal adaption, fracture of the restoration were scored using a modified United States Public Health Service (USPHS) criterion.
- Dental plaque accumulation and gingival condition were assessed using plaque index (PI) and GI.
- Preparation time and cementation assessment using stop watch to record time from preparation start till final restoration cementation.⁽¹⁵⁾

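### The plan does not say which error variance is used for normally distributed outcomes; Welch's ANOVA with unpooled intervals for each contrast would protect against unequal spread at small cost

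*Combined protocol and SAP*

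**What the plan says.** The Data Management and Analysis section sets out this route for numeric outcomes:

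- Assumption check: "Data will be explored for normality using Kolmogorov-Smirnov test and Shapiro-Wilk test". No check or allowance for unequal variances is given.
- Normal data: "Comparisons between 3 groups for normally distributed numeric variables will be done using the ANOVA". ANOVA is unqualified, and no Welch version or post-hoc method is named.
- Non-normal data: "for non-normally distributed numeric variables will be done by Kruskal Wallis test". The switch depends on normality, not on spread.
- Equivalence: "An equivalence limit will be checked in the difference between groups". No interval formula, error term or degrees of freedom are given.
- Level: "A p-value less than or equal to 0.05 will be considered statistically significant", and "All tests will be two tailed".

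The Sample Size calculation section describes an equivalence trial. It says "22 patients in each group are required to be 80% sure" that a two-sided 95% interval will exclude a mean difference above 0.6, and it raises the number to 24 per group for losses. It states no SD, common or per arm.

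The Observations section includes one outcome that could plausibly reach ANOVA with unequal spread: "Preparation time and cementation assessment using stop watch to record time from preparation start till final restoration cementation".

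**The concern.** Ordinary ANOVA estimates one error variance from all three arms. The arms differ in procedure. Under Restoration of the tooth, endocrowns go through chamber preparation, scanning, CAD/CAM manufacture, etching and silane, and resin cementation, while the other two arms receive a preformed crown luted with glass ionomer. A wider spread of procedure times in the endocrown arm would be unsurprising.

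If one arm is more variable and its variance enters a common error term, that term is too small for contrasts involving the arm and too large for the contrast that leaves it out. Both contrasts with the zirconia control could then carry the wrong uncertainty, in opposite directions. This matters because the sample size rests on a confidence interval for a mean difference, and the analysis section does not define that interval.

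**Working it through.** **1. The plan's own figure.** For equivalence with a true difference of 0, a two-sided 95% interval and 80% power (beta split over two sides):

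n = 2 × SD² × (1.960 + 1.282)² / 0.6² = 58.37 × SD²

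SD 0.6 gives 58.37 × 0.36 = 21.01, rounded up to 22. Any SD from 0.600 to 0.614 gives 22. Because the plan states no SD, 22 is consistent with an SD of about 0.6 but cannot be confirmed. The rest of the working takes SD 0.6 for Bioflex and zirconia, and r times that for endocrown, with r = 1, 1.5, 2 and 3. All of these are assumptions.

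**2. Algebra with equal arms and the three-group error.** In units of the smaller variance, the pooled variance is (r² + 2)/3.

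- Endocrown minus zirconia: pooled SE / true SE = √[2(r² + 2) / (3(r² + 1))]. At r = 2 this is √(12/15) = 0.89, too small.
- Bioflex minus zirconia: √[(r² + 2)/3]. At r = 2 this is √2 = 1.41, too large.

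**3. Simulation (200,000 normal trials per scenario, 22 per arm).**

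| Endocrown SD ratio | 1 | 1.5 | 2 | 3 |
|---|---|---|---|---|
| Coverage, endocrown-zirconia, three-group error (%) | 95.0 | 93.2 | 92.0 | 90.3 |
| Coverage, Bioflex-zirconia, three-group error (%) | 95.1 | 97.9 | 99.3 | 99.9+ |
| Overall type I error, ANOVA (%) | 5.0 | 5.5 | 6.2 | 7.4 |
| Chance of showing Bioflex-zirconia equivalence, true difference 0, three-group error (%) | 80.9 | 64.4 | 37.9 | 2.9 |

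With unpooled (Welch-Satterthwaite) intervals, coverage at ratio 2 is 95.0% for both contrasts, and the chance of showing Bioflex-zirconia equivalence stays at about 80% throughout. Welch's test has type I error of 4.9% to 5.1%. Repeat simulations gave ANOVA type I error within about 0.3 points of the table. Results at 24 per arm show the same pattern.

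**4. If each interval instead pools only the two groups compared.**

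- Equal arms, ratio 2: pooled variance (4 + 1)/2 = 2.5, so SE² = 2.5 × 2/n = 5/n, which is the true value. Only the degrees of freedom are off, and coverage is 94.8%.
- Evaluable 18 endocrown and 24 zirconia, ratio 2: pooled variance (17 × 4 + 23 × 1)/40 = 2.275; SE² = 2.275 × (1/18 + 1/24) = 0.221. The true value is 4/18 + 1/24 = 0.264. The SE ratio is √(0.221/0.264) = 0.92, and simulated coverage is 92.5%.
- The reverse, 24 and 18: pooled variance (23 × 4 + 17 × 1)/40 = 2.725; SE² = 0.265 against a true 4/24 + 1/18 = 0.222. The SE ratio is 1.09, so the interval is too wide.

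With 18/22/24 evaluable and ratio 2, three-group pooled coverage for endocrown-zirconia falls to 89.1% and ANOVA type I error rises to 8.2%. The Welch versions stay at 94.9% and 5.1%.

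**5. Power of the overall test, in both directions (ratio 1.5 / 2 / 3).**

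- Bioflex differs from zirconia by 0.5, endocrown mean equal to zirconia: ANOVA 66.5 / 50.1 / 27.0%, Welch 74.0 / 70.8 / 68.1%.
- Only endocrown differs, by 0.9 SD of the other arms: ANOVA 68 / 52 / 33%, Welch 58 / 39 / 20%.

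**6. Cost if the SDs are equal.** Overall power for a difference of 0.5 goes from 80.4% to 79.4%, equivalence power from 80.8% to 79.8%, and intervals widen by about 1%.

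**The case against.** A reader might infer that the planned intervals are wrong in opposite directions. The documents do not support that. No SD appears anywhere, so unequal spread is plausible but not shown. Nor does the plan say that differences use the three-group error. The sample size is framed as a comparison of a standard with an experimental treatment, which fits a two-group interval at least as well, and step 4 shows that such an interval is nearly correct with equal arms. This objection stands, so the interval problem is conditional.

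A reader might also infer that ANOVA generally hides differences that Welch's test would find. Step 5 shows that this depends on which arm differs. If only endocrown differs, ANOVA rejects more often, partly because its type I error is inflated. Extra endocrown steps would be expected to shift that arm's mean procedure time as well as its spread, so this case is realistic.

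The unequal-loss case is limited too. A fall to 18 of 24 is a 25% loss (6/24), against the planned allowance of 8.3% (2/24), and the error reverses if the losses fall in the less variable arm. Procedure time is recorded at placement, so follow-up losses do not affect it. The plan gives no reason to expect unequal spread in the outcomes measured later.

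Finally, ordinal scores and raw counts may fail normality and go to Kruskal-Wallis, which this change does not touch. What remains is that the plan leaves the error term open, and that an option holding nominal error rates in every scenario examined is available at small cost.

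**Conclusion.** The point holds as a low-cost improvement. The plan names ordinary ANOVA, checks normality only, and leaves undefined the error variance behind its equivalence check.

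The size depends on two things the documents do not settle: whether one arm is more variable (ratios of 1.5 to 3 are assumed), and whether differences use the three-group error. If both hold, endocrown-zirconia coverage is about 93 / 92 / 90%, and Bioflex-zirconia coverage runs from 98% to nearly 100%. The ANOVA type I error, about 5.5 / 6 / 7%, depends only on the unequal spread. If two-group pooling is used with equal arms, the interval error almost disappears.

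Unpooled analysis restores validity, not precision. At ratio 2 the chance of showing endocrown-zirconia equivalence when the true difference is 0 is 11% with correctly sized intervals, against 25% with the too-narrow pooled ones. The conclusion is limited to numeric outcomes judged normal.

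**What to change.** In Data Management and Analysis, state that:

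- the three-group test for normally distributed numeric outcomes will be Welch's ANOVA, chosen in advance and not conditional on a preliminary variance test;
- each mean difference from zirconia will be reported with an unpooled (Welch-Satterthwaite) two-sided 95% confidence interval from the two groups compared and, for the outcome to which the 0.6 limit applies, judged against that limit. The plan should name that outcome and give the SD behind 22 per group.

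Games-Howell should not be used for the equivalence intervals. It is simultaneous, with a critical value of 2.43 against 2.02 at 22 per arm (2.43/2.02 = 1.20, so about 20% wider). With equal SDs of 0.6 it would cut the chance of showing equivalence for one pair from about 80% to 62%.

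The change takes two sentences and leaves the sample size as it is. It costs about 1 point of power and about 1% in interval width if variances are equal. If the endocrown arm is more variable, the overall test loses about 10 to 13 points of power for an endocrown-only difference, part of which reflects ANOVA's inflated error.
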